5.4 Screen Failures

A screen failure is defined as a potential participant who signed the informed consent form (ICF), but did not meet one or more criteria required for participation in the study and was not randomized.

For screen failures, the demographic data, date of signing the ICF, inclusion and exclusion criteria, AEs up to the time of screen failure and reason for screen failure will be collected in the electronic data source.

5.4.1 Rescreening

Results of screening assessments that do not meet the parameters required by eligibility criteria (e.g., clinical laboratory tests, vital signs, physical examination, ECG, etc.) may be repeated once within the 28-day screening period without the need to register the participant as a screen failure. If the participant meets exclusion criteria that cannot resolve during the screening period, or more than 28 days elapse from the date of signing the ICF, the participant must be documented as a screen failure. In order to re-screen after prior screen failure, a new ICF must be signed and the participant entered into screening with a new participant identification number. Rescreening is only allowed once for an individual participant.

6 INVESTIGATIONAL PRODUCT(S)

6.1 Investigational Product(s) Administered

Table 4 Investigational Product(s)

IP Name	ASP8062	Placebo ASP8062	Morphine sulfate
Use	Test product	Placebo for ASP8062	Test product
Dosage Form	Tablet	Tablet	Immediate-release tablet
Physical Description	Round, light yellowish-red film coated tablet	Round, light yellowish-red film coated tablet	White, biconvex tablet scored on 1 side and product identification "54" over "733" debossed on the other side
Unit Dose Strength	25 mg (1 × 25 mg tablet)	NA (1 × tablet)	45 mg (3 × 15 mg immediate-release tablets)
Frequency	Once daily	Once daily	Single dose
Duration	10 days	10 days	1 day
Packaging and Labeling	1 × aluminum/aluminum blister strips (2 × 7 configuration per strip in carton)	1 × aluminum/aluminum blister strips (2 × 7 configuration per strip in carton)	100 tablets (10 × 10) unit-dose tablets, packaged in carton
Route	Oral	Oral	Oral
Administration	On days 1, 9 and 10, ASP8062 or placebo will be administered orally under fasting conditions (i.e., no food or beverage will be allowed from at least 10 hours predose through at least 4 hours postdose) with approximately 240 mL water. Water intake will be prohibited from at least 1 hour predose through at least 1 hour postdose, except for the approximately 240 mL water to swallow the IP. On all other dosing days, ASP8062 or placebo will be administered orally under standardized fed conditions (i.e., meals will be served up to 1 hour predose or at least 2 hours postdose) with approximately 240 mL water. Water will be allowed ad libitum.		On day 10, morphine will be administered orally under the existing fasting conditions with approximately 240 mL water, immediately after the ASP8062 or placebo dose. Water intake will be prohibited from at least 1 hour predose through at least 1 hour postdose, except for the approximately 240 mL water to swallow the IP.
IMP or Non-IMP	IMP	IMP	IMP
Sourcing	Provided centrally by sponsor	Provided centrally by sponsor	Provided locally by investigator site

IMP: Investigational Medicinal Product; IP: investigational product

6.2 Preparation/Handling/Storage/Accountability

6.2.1 Packaging and Labeling

All IP used in this study will be prepared, packaged and labeled under the responsibility of qualified personnel at Astellas Pharma Global Development Inc. (APGD) or sponsor's designee in accordance with APGD or sponsor's designee standard operating procedures (SOPs), current Good Manufacturing Practice (GMP) guidelines, International Council for

Harmonisation of Technical Requirements for Pharmaceuticals for Human Use (ICH) Good Clinical Practice (GCP) guidelines and applicable local laws/regulations.

Each carton will bear a label conforming to regulatory guidelines, GMP and local laws and regulations that identifies the contents as investigational drug.

6.2.2 Handling, Storage and Accountability

- The investigator or designee must confirm appropriate temperature conditions have been maintained during transit for all IP received and any discrepancies are reported and resolved before use of the IP.
- Only participants enrolled in the study may receive IP and only authorized study site personnel may supply or administer IP. Only IP with appropriate expiry/retest dating may be dispensed.
- All IP must be stored in a secure, environmentally controlled and monitored (manual or automated) area in accordance with the labeled storage conditions and access must be limited to the investigator and authorized study site personnel.
- The investigator, institution or the head of the medical institution (where applicable) is responsible for accountability, reconciliation and record maintenance (i.e., receipt, reconciliation and final disposition records).
- After final reconciliation is confirmed, further guidance and instruction of used and unused IP will be provided.

6.3 Randomization and Blinding

6.3.1 Blinding Method

The study will be conducted as participant- and investigator-blinded.

In order to maintain the blind, the participants will receive the same number of tablets. The pharmacist will provide the investigator or designee with blinded IP to participants.

6.3.2 Confirmation of the Indistinguishability of the Investigational Product

The appearance of both the dosage form and packaging of ASP8062 are identical to those of its placebo.

6.3.3 Retention of the Assignment Schedule and Procedures for Treatment Code Breaking

The randomization list will be stored with the clinical unit pharmacist in a locked storage facility. The individual emergency code envelopes (ECEs) will be stored with medical staff for medical emergency use.

6.3.4 Breaking the Treatment Code for Emergency

For every randomized participant, an individual ECE will be stored in a secure location with access by designated personnel, in the event of a medical emergency requiring knowledge of the treatment assigned to the participant. A code break can only be requested by the investigator or subinvestigators designated to have access to perform blind-breaking. In case of a medical emergency, the investigator (or his/her designated backup) has the sole

responsibility for determining if unblinding of the participant's treatment assignment is warranted. Participant safety must always be the first consideration in making such determination. If the investigator decides that unblinding is warranted, the investigator should make every effort to contact the sponsor prior to unblinding a participant's treatment assignment unless this could delay emergency treatment for the participant.

The investigator must have a designated backup to support emergency unblinding requirements.

Prior to randomization, participants should be provided with information that includes the study site emergency contact number and backup contact number in case of a medical emergency. Any unblinding by the investigational personnel must be reported immediately to the sponsor and include an explanation of why the IP was unblinded. Personnel who will be unblinded will not convey information regarding treatment assignments in the study, whether informally or formally, to any other person, unless required for medical reasons. The time and date of opening, any of these ECEs must be documented in the study file and the medical monitor should be contacted to discuss the case, if possible, before unblinding. If unblinding is associated with a serious adverse event (SAE), the investigator is to follow the instructions in [Section 10.3.7 Appendix 3 Reporting Procedures for Serious Adverse Events].

All unopened ECEs will be destroyed at the end of the study. Opened ECEs will remain at the study site with the participant's study records.

6.3.5 Breaking the Treatment Code by the Sponsor

The sponsor may break the treatment code for participants who experience a suspected unexpected serious adverse reaction (SUSAR), in order to determine if the individual case or a group of cases requires expedited regulatory reporting. Individual emergency codes will be provided to the limited personnel who are responsible to break the codes for all SUSAR cases for reporting purposes.

6.3.6 Assignment and Allocation

6.3.6.1 Participant Number

Participants will be assigned a participant number at study entry (i.e., signing of informed consent). The participant numbers will be sequential and rising.

The participant number will comprise of a 5-digit clinical unit number and 5-digit screening number.

6.3.6.2 Randomization

Prior to dosing, participants will be assigned a randomization number in accordance with the randomization code generated by the sponsor's Data Science department or designee.

Participants will be randomized in a 2:1 ratio to ASP8062 or placebo.

Once a randomization number has been allocated to a participant, it will not be assigned to another participant. If a participant withdraws prematurely from the study and is replaced

under the direction of the sponsor, then a replacement randomization number will be assigned. A replacement randomization code will be generated such that replacement participants are assigned to the same treatment as the discontinued participant.

6.4 Investigational Product Compliance

Dosing will take place in the clinical unit. The administration of IP will be supervised to ensure treatment compliance. After IP administration, a check of the participant's mouth and hands will be performed. The exact day and time of IP administration will be documented.

6.5 Dose Modification

Dose modifications are not allowed.

6.6 Continued Access to Investigational Product After the End of the Study

Not applicable.

6.7 Treatment of Overdose

In the event of suspected ASP8062 overdose, the participant should receive supportive care and monitoring. The medical monitor/expert should be contacted as applicable.

In the event of suspected morphine overdose, refer to the approved package insert, summary of product characteristics or local product information supplied by the manufacturer for the IP. The medical monitor/expert should be contacted as applicable.

Refer to [Section 10.3.8 Appendix 3 Reporting Procedures for Special Situations] for reporting requirements for suspected overdose or other medication error.

6.8 Concomitant Therapy

All medicinal products, including prescribed and nonprescribed drugs used prior to IP administration will be considered previous medication.

Specific restrictions on previous medications are provided in [Section 5.2 Exclusion Criteria].

All medication taken within 4 weeks prior to admission to the clinical unit will be documented.

All medicinal products other than the IP(s), including prescribed or nonprescribed drugs (including vitamins and natural and herbal remedies, e.g., St. John's Wort), used from first IP administration until the ESV will be considered concomitant medication.

Participants will only be allowed to use the following concomitant medication, if needed, from first IP administration until the ESV:

- Acetaminophen (up to 2 g/day)
- Topical dermatological products, including corticosteroid products
- Hormonal contraceptives
- HRT

If a participant's health condition necessitates the use of any medication other than the permitted medications during the study, an investigator and medical monitor, or designee(s), will discuss the case and determine if the participant should be withdrawn from the study and/or excluded from analysis sets, depending on if, and how, the medication(s) used influence(s) the study outcome. The nonpermitted concomitant medication will be recorded as a protocol deviation.

All concomitant treatments (medication and nonmedication therapy) will be documented.

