3 OBJECTIVES, ENDPOINTS AND ESTIMANDS

Table 3 Study Objectives and Endpoints

Objectives	Endpoints
Primary	
• To assess the safety and tolerability of multiple doses of ASP8062 or placebo alone and in combination with a single dose of morphine• Nature, frequency and severity of AEs• Clinical laboratory tests (hematology, biochemistry and urinalysis)• Vital signs (blood pressure, pulse and respiratory rate)• 12-lead ECG• C-SSRS• SpO₂• End tidal CO₂
Secondary	
• To assess the potential for pharmacokinetic interaction between ASP8062 and morphine• Plasma ASP8062: AUC₂₄ and C_{max}• Plasma morphine and its metabolites (M3G and M6G): AUC_{inf}, AUC_{last} and C_{max}
Exploratory	
• To assess additional safety and tolerability of multiple doses of ASP8062 or placebo alone and in combination with a single dose of morphine• Oral temperature• ARCI-49• To assess the general pharmacokinetic parameters of ASP8062, its metabolites, morphine and its metabolites• Plasma ASP8062: CL/F, t_{1/2}, t_{max}, t_{lag}, V_z/F, C_{trough} and PTR• Plasma ASP8062 metabolites (AS3486189, AS3486191 and AS3486192): C_{max}, AUC₂₄, t_{1/2}, t_{max}, t_{lag}, V_z/F, C_{trough} and PTR• Plasma morphine and its metabolites (M3G and M6G): AUC_{inf}(%extrap), CL/F (morphine), t_{1/2}, t_{max}, t_{lag} and V_z/F• Plasma ASP8062 metabolites (AS3486189, AS3486191 and AS3486192): AUC₂₄ and C_{max}

AE: adverse event; ARCI-49: 49-item short form of Addiction Research Center Inventory scale; CO₂: carbon dioxide; C-SSRS: Columbia-suicide severity rating scale; ECG: electrocardiogram; M3G: morphine-3β-D-glucuronide; M6G: morphine-6β-D-glucuronide; SpO₂: blood oxygen saturation

Estimands

Not applicable.

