7.3.6 Adverse Events of Special Interest

AEs of special interest are AEs the sponsor may wish to carefully monitor. These AEs may be serious or nonserious and should be reported on the electronic data source and the SAE worksheet. These AEs are not considered SAEs unless they meet the definition of an SAE.

AEs related to potential substance abuse and suicide (serious or nonserious) are considered to be of scientific and medical concern specific to ASP8062, for which ongoing monitoring and reporting is required.

Additional information around AEs of special interest will be collected to complete participant narratives. AEs of special interest related to potential substance abuse are listed in [Section 10.10 Appendix 10 Adverse Events of Interest Related to Potential Substance Abuse and Following Drug Withdrawal].

AEs of special interest with respect to morphine include respiratory depression, constipation, nausea, vomiting, sedation, somnolence, lightheadedness, dizziness, and sweating.

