9.3 Populations for Analyses

For each treatment group, the number and percentage of participants will be characterized for all randomized participants and by each population.

The following populations are defined:

Population	Description
Randomized	All participants who are randomized. Participants will be analyzed according to the study treatment to which they are randomized.
SAF	All participants randomly assigned to study IP and who take at least 1 dose of study IP. Participants will be analyzed according to the IP they actually received. The SAF will be used for all summaries and analysis of the safety data.
PKAS	All participants who receive at least 1 dose of IP for which concentration data are available to facilitate derivation of at least 1 primary pharmacokinetic parameter. Inclusion of participants in the PKAS with missing data or major protocol deviations will be considered by the pharmacokineticist on a case-by-case basis. The PKAS will be used for all summaries and analyses of the pharmacokinetic data.

IP: investigational product; PKAS: pharmacokinetic analysis set; SAF: safety analysis set

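### Could the concomitant-medication rule in section 6.8 remove participants from the safety analysis set?

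*Combined protocol and SAP*

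**What the plan says.** Section 6.8 (Concomitant Therapy) permits four kinds of product during the study: acetaminophen up to 2 g/day, topical dermatological products, hormonal contraceptives and HRT. If anything else is needed, "an investigator and medical monitor, or designee(s), will discuss the case" and decide whether the participant is withdrawn and/or "excluded from analysis sets, depending on if, and how, the medication(s) used influence(s) the study outcome". The use is recorded as a protocol deviation, with no grading.

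Section 9.3 (Populations for Analyses) defines three populations. Its footnote gives the name analysis set to two of them: "PKAS: pharmacokinetic analysis set; SAF: safety analysis set". The SAF is "All participants randomly assigned to study IP and who take at least 1 dose of study IP", and "The SAF will be used for all summaries and analysis of the safety data". For the PKAS only, 9.3 adds: "Inclusion of participants in the PKAS with missing data or major protocol deviations will be considered by the pharmacokineticist on a case-by-case basis".

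The primary objective in section 3 is "To assess the safety and tolerability of multiple doses of ASP8062 or placebo alone and in combination with a single dose of morphine", so the primary endpoints are summarized on the SAF.

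**The concern.** The permitted list is short. Section 7.3.6 states that "AEs of special interest with respect to morphine include respiratory depression, constipation, nausea, vomiting", among others, and drug treatment of such an event would usually fall outside the four permitted product types. The way into the 6.8 discussion could therefore be the adverse event itself.

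Section 6.8 speaks of sets in the plural, names none, and makes influence on the study outcome the test. In a trial whose primary objective is safety, that outcome can be read to include safety. Since 9.3 calls only the SAF and the PKAS analysis sets, the literal wording covers both. Applied to the SAF, it would be an outcome-dependent exclusion: participants would leave the safety summaries because they had the events being counted, and incidence would be biased downward. The arms are small, so one exclusion would be visible. No sentence in the document says which section prevails.

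**Working it through.** The question turns on wording, and the plan states no figure to reproduce. The two sections compare as follows.

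| Point | Section 6.8 | Section 9.3 |
|---|---|---|
| Which set | Plural, none named | SAF without any exclusion clause; discretion for the PKAS only |
| Who decides | Investigator and medical monitor, or designees | Pharmacokineticist |
| Trigger | Non-permitted medication, recorded as a deviation without grade | Missing data or major protocol deviations |

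**Which section an analyst would follow.** Section 9.3 is where the populations are defined. Its SAF rule rests on two facts, randomization and at least one dose, and a later co-medication alters neither. The same row requires the SAF for all safety summaries. Sections 9.4.1 and 9.4.3.3 refer to the SAF without any exception for concomitant medication. Section 6.8 does not say that it modifies 9.3.

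**Whether 6.8 has a sensible reading beside 9.3.** It does. Asking whether a drug influences the outcome is the natural question for pharmacokinetic data. Section 2.1 describes ASP8062 as mainly metabolized by CYP3A4, so a co-medication can alter exposure and make a profile unsuitable. Section 9.3 already provides for that judgement. The 6.8 discussion can feed the pharmacokineticist's decision, and the two sections then fit together.

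**Size under the literal reading.** Inputs: about 24 participants (9.2), allocated 2:1 (6.3.6.2).

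- ASP8062: 24 × 2/3 = 16. Placebo: 24 × 1/3 = 8.
- One participant is 1/16 = 6.3% or 1/8 = 12.5% of an arm.
- If the only participant with a given event were excluded, 1/16 would become 0/15, or 1/8 would become 0/7.

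Section 9.4.3 uses four safety groups, and the two morphine groups hold only those dosed on day 10. For events after morphine the denominators may therefore be smaller. If only the minimum of 18 completers (9.2) reached that point and the ratio held, they would be 18 × 2/3 = 12 and 18 × 1/3 = 6, and one participant would be 1/12 = 8.3% or 1/6 = 16.7%.

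The 5% cut-off in 9.4.3.1 adds nothing to this. It equals 0.05 × 16 = 0.8 and 0.05 × 8 = 0.4 of a participant, so a single case passes it in either arm. On the natural reading it applies only to the table of TEAEs excluding SAEs, while the overall and IP-related TEAE summaries have no threshold. A participant kept in the SAF is counted there in any case.

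The documents give no rate of non-permitted medication use, so the number of participants affected cannot be estimated.

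**What would remain visible.** AE data are listed (9.4.3.1). AEs of special interest are followed up (7.3.3) and narrated (7.3.6). The stopping criteria in 8.4 count ASP8062-treated participants, not SAF members.

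**The case for a change.** The best case for a change is that 6.8, as written, gives two people authority to exclude a dosed participant on a criterion that can include safety. The investigator is blinded. The document does not say whether the medical monitor is, and 6.8 sets no deadline relative to release of the treatment codes. Two or three sentences would close the gap, with no effect on data collection. Even if 9.3 prevails for the SAF, the sections still disagree for the PKAS on who decides and on how serious the deviation must be, and the PKAS supports the secondary objective.

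Part of this stands. The wording differs on scope, decision-maker and trigger, and no precedence rule is written. The step from there to a flaw in the safety analysis does not stand. It needs an unspecific phrase in a concomitant-therapy paragraph to override the definition of the population and the explicit instruction to use it for all safety data. The absence of a precedence clause between a passing mention and a definition is ordinary drafting. On the PKAS, 9.3 names the decision-maker and asks for case-by-case judgement, and input from the investigator and medical monitor is compatible with that. A rule to document exclusions before the codes are released would be good practice, but nothing in the plan contradicts it. The study is descriptive and unpowered, with no hypotheses (9.1, 9.2), so no error rate depends on the point.

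**Conclusion.** No change to the plan is needed. Section 6.8 is loosely worded, and analysts would fill the gap sensibly by building the SAF from 9.3 and leaving any medication-related exclusion to the pharmacokineticist's review of the PKAS. On that reading nobody leaves the SAF and every safety summary is unchanged.

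This rests on 9.3 governing as the defining section. That is an inference, though a strong one, because 9.3 states both the SAF definition and its mandatory use. If the inference failed, the exposure would be to summary counts and denominators only: one participant in about 16 or 8 per exclusion, with the event still listed. The differences in decision-maker and deviation grade are clerical. They could be tidied by a cross-reference to 9.3 if the protocol were amended for another reason, but they do not justify an amendment of their own.

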7 STUDY PROCEDURES AND ASSESSMENTS

- Study procedures and their timing are summarized in the Schedule of Assessments [Table 1]. Adherence to the study design requirements, including those specified in the Schedule of Assessments [Table 1], is essential and required for study conduct. Prospective protocol waivers or exemptions are not allowed.
- Any change, divergence or departure from the study design or procedures identified in the protocol is considered a protocol deviation. All deviations from the protocol are to be recorded.
- Immediate safety concerns should be discussed with the sponsor immediately upon occurrence or awareness to determine if the participant should continue or discontinue study treatment.
- All screening evaluations must be completed and reviewed to confirm that potential participants meet all eligibility criteria. The investigator will maintain a screening log to record details of all participants screened and to confirm eligibility or record reasons for screening failure, as applicable.
- Procedures conducted as part of the participant's routine clinical management (e.g., imaging, blood count) and obtained before signing of the ICF may be utilized for screening or baseline purposes provided the procedures met the protocol-specified criteria and were performed within the time frame defined in the Schedule of Assessments [Table 1].
- Analyte results that could unblind the study will not be reported to investigative sites or other blinded personnel until the study has been unblinded.

